1. PROTOCOL SUMMARY

Study Title	A pilot randomized, double-blind, placebo-controlled trial to investigate the anti-inflammatory effects of Frondanol in adults with inflammatory bowel disease
Internal ref. no. (or short title)	Frondanol in IBD
Study Design	This is a pilot, prospective, double-blinded, two-arm, randomized controlled trial of the efficacy of Frondanol in comparison to placebo in decreasing bowel inflammation in patients with a clinical diagnosis of IBD who are in remission and on standard of care treatment.
Study Participants	
Inclusion criteria: A confirmed clinical diagnosis of IBD of any duration, age 18 years or older, with mild to moderate disease and on standard therapy. The diagnostic criteria for IBD include the presence of chronic diarrhoea for more than four weeks, and evidence of active inflammation on endoscopy and chronic changes on biopsy. Patients with stable mild to moderate IBD will be eligible for the study. Stable IBD is defined as having stable symptoms over a period of several weeks, diagnostic evaluation has been completed and the patient has been on consistent medication. Mild to moderate IBD is indicated by a Partial Mayo score (Mayo Clinic Score/Disease Activity Index for Colitis) of between 1-6, and a total of Mayo score of 1-10 (Pabla and Schwartz, 2020). For patients with Crohn's disease, only those with Crohn's colitis will be included (patients with small bowel disease are eligible to enter the trial as long as they also have large bowel inflammation).
 
Exclusion criteria: Pregnancy, breastfeeding, allergy to seafood or marine products, severe medical illness such as uncontrolled diabetes ($\text{HbA1C} > 10$), significant or unstable cardiovascular or pulmonary disease, impaired renal function ($\text{Cr} > 2.0 \text{mg/dL}$), current or recent ($< 1 \text{ year}$) malignancy, or other significant medical illness that in the view of the investigators may impair participation in the study. Patients with severe IBD (defined by a Partial Mayo score of 7-9 and a total Mayo score of 11-12 (Pabla and Schwartz, 2020), with active symptoms) will not be eligible to participate in the study.
 
Reference:

RJ

Version 3.2. Effective Date: 04 December 2021

Planned Size of Sample (if applicable)	100 patients (50 per arm) with stable IBD will be recruited into this pilot study.
Follow up duration (if applicable)	Six months
Planned Study Period	Two years
Research Question/Aim(s)	
1) To compare plasma levels, biopsy mRNA (using low density expression arrays) and protein (using either Luminex or Western blotting) levels of the following parameters between IBD patients treated with Frondanol and those treated with placebo at baseline and after six months of treatment:
 
a) Cytokines: TNFα, IL1β, IL6, IL17A, IL21, IL22, IL23, IFNγ, IFNα, as well as vascular endothelial growth factor (VEGF-A), MIP-1, MIP-2;
 
b) Markers of inflammation: Myeloperoxidase, calprotectin, S100A12, β2-microglobulin, amyloid A (A-SAA), intercellular adhesion molecule 1 (ICAM-1), vascular cell adhesion molecule 1 (VCAM-1), MIP-2α (CXCL2), MCP-1 (CCL2). Leukotriene B4 (LTB4), 5-hydroxyeicosatetraenoic acid (5-HETE) and prostaglandin E2 (PGE2) will be measured by specific ELISA assays.
 
2) To compare the following routine clinical parameters between IBD patients treated with Frondanol and those treated with placebo at baseline and after six months of treatment:
 
a) Patient symptoms;
 
b) Blood: Complete blood count (CBC), erythrocyte sedimentation rate (ESR), C-reactive protein (CRP), albumin;
 
c) Stool: Fecal calprotectin level;
 
d) Endoscopic and histologic features.
 
3) To compare in-vitro concentration-dependent responses to Frondanol and placebo on inflamed organoids by measurement of cytokines and other inflammatory markers, in particular 5-HETE, LTB4 and PGE2.

RJ

Version 3.2. Effective Date: 04 December 2021

2. ABBREVIATIONS

5-HETE	5-hydroxyeicosatetraenoic acid
CBC	Complete blood count
CRP	C-reactive protein
DCF	Data Collection Form
DHCR	Dubai Healthcare City Authority-Regulation
ELISA	Enzyme-linked immunosorbent assay
ESR	Erythrocyte sedimentation rate
IBD	Inflammatory bowel disease
ICAM-1	Intercellular adhesion molecule 1
IFN	Interferon
IL	Interleukin
LOX	Lipoxygenase
LTB4	Leukotriene B4
MCH	Mediclinic City Hospital
MCME	Mediclinic Middle East
PGE2	Prostaglandin E2
REC	Research & Ethics Committee
TNF	Tumor necrosis factor
VCAM-1	Vascular cell adhesion molecule 1

RJ

[figure not shown]
Version 3.2. Effective Date: 04 December 2021

Introduction

3. BACKGROUND

Inflammatory bowel disease (IBD), consisting of Crohn's disease and ulcerative colitis, is a debilitating condition, particularly during active periods (flares) of the disease and can sometimes lead to life-threatening complications (1). The prevalence of IBD has rapidly increased worldwide; it affects between one in 200 and one in 300 individuals in high-income countries, and despite its incidence being lower in low-middle income countries, this has also been rapidly increasing (2, 3). The highest reported prevalence in the Middle East is one in 1,800 for Crohn's disease and one in 1,000 for ulcerative colitis (3).

IBD is characterized by chronic gut inflammation resulting in symptoms such as severe diarrhea, abdominal pain, blood in stool, fatigue and unintended weight loss, which significantly affect the quality of life of patients (1). Although the exact mechanism underlying the chronic gut inflammation is not fully understood, several cytokine networks are thought to be involved (4-6). The cytokine networks underlying the progression of IBD are depicted below in Figure 1 (4).

RJ

Version 3.2. Effective Date: 04 December 2021

Figure 1: Cytokine networks underlying the progression of IBD (4)

Currently, treatment of IBD relies on minimizing symptoms and improving quality of life through the control of disease progression and complications; however, these drugs have significant systemic side effects that reduce their tolerability (7). Moreover, up to 40% of patients still exhibit non-response to therapy, and these treatment-refractory patients would require alternative therapeutic approaches (8, 9).

Sea cucumbers and their extracts have been reported to have high nutritional value and several potential health benefits including anti-inflammatory effects, and used for centuries as folk medicine or traditional foods in countries such as Japan, Indonesia, Korea and China (10, 11). Frondanol, a widely available neutraceutical extract of the edible sea cucumber, *Cucumaria frondosa*, has been reported to possess potent chemopreventive and anti-inflammatory effects in both animals and humans (12-15), whilst showing no signs of toxicity (12, 16). The potent anti-inflammatory effects of Frondanol in a mouse model of IBD provide encouragement for investigating its effects in human IBD patients (15).

Over the past 25 years, it is estimated that more than three million Frondanol capsules have been consumed on the human market with no reported side effects. An even larger amount has been consumed on the veterinary market without a single reported incident. If proven beneficial, Frondanol, will be a useful supplement in treating the underlying chronic gut inflammation in IBD patients, increasing the likelihood of patients remaining in remission and potentially providing an effective, natural and safe treatment for treatment naive patients in the future.

The proposed study is a pilot, double-blinded, placebo-controlled trial of Frondanol in patients with IBD (Crohn's disease or ulcerative colitis) who are currently in remission and are on standard therapy. One hundred patients will be randomized (1:1) to receive Frondanol or placebo as an adjunct to their standard therapy for the period of six months. Blood and tissue samples from colon biopsies obtained during routine visits and endoscopies at baseline and six months later will be collected. The levels of inflammatory markers such as myeloperoxidase, tumor necrosis factor (TNF)- α , interleukin (IL)1 β , IL6, IL17A, IL22, interferon gamma (IFN- γ) and several other inflammatory markers will be compared between patients treated with Frondanol and those treated with placebo, and the findings will be correlated with clinical and histological parameters. In addition, we plan to develop a stem cell-derived gut organoid model to investigate the mechanism of action of Frondanol.

4. RATIONALE

RJ

Version 3.2. Effective Date: 04 December 2021

The overall aim of this project is to investigate the anti-inflammatory effects of Frondanol on bowel inflammation in patients with IBD.

5. RESEARCH OBJECTIVES

- 1) To compare plasma levels, biopsy mRNA (using low density expression arrays) and protein (using either Luminex or Western blotting) levels of the following parameters between IBD patients treated with Frondanol and those treated with placebo at baseline and after six months of treatment:
 - a) Cytokines: TNF α , IL1 β , IL6, IL17A, IL21, IL22, IL23, IFN γ , IFN α , as well as vascular endothelial growth factor (VEGF-A), MIP-1, MIP-2;
 - b) Markers of inflammation: Myeloperoxidase, calprotectin, S100A12, β 2-microglobulin, amyloid A (A-SAA), intercellular adhesion molecule 1 (ICAM-1), vascular cell adhesion molecule 1 (VCAM-1), MIP-2 α (CXCL2), MCP-1 (CCL2). Leukotriene B4 (LTB4), 5-hydroxyeicosatetraenoic acid (5-HETE) and prostaglandin E2 (PGE2) will be measured by specific ELISA assays.
- 2) To compare the following routine clinical parameters between IBD patients treated with Frondanol and those treated with placebo at baseline and after six months of treatment:
 - a) Patient symptoms;
 - b) Blood: Complete blood count (CBC), erythrocyte sedimentation rate (ESR), C-reactive protein (CRP), albumin;
 - c) Stool: Fecal calprotectin level;
 - d) Endoscopic and histologic features.
- 3) To compare in-vitro concentration-dependent responses to Frondanol and placebo on inflamed organoids by measurement of cytokines and other inflammatory markers, in particular 5-HETE, LTB4 and PGE2.

6. STUDY DESIGN/METHODOLOGY

5.1 Design overview

This is a pilot, prospective, double-blinded, two-arm, randomized controlled trial of the efficacy of Frondanol in comparison to placebo in decreasing bowel inflammation in patients with a clinical diagnosis of IBD who are in remission and on standard of care treatment.

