6.3 Sample and recruitment

All eligible IBD patients visiting Gastroenterology Department of any of the study centres that will participate in patient recruitment (Mediclinic City Hospital, Mediclinic Parkview Hospital and Rashid hospital) under the care of any of the coinvestigator consultant gastroenterologists during the period of recruitment (12 months from the start date of the study – to be decided following ethical approval) will be offered to take part in the study.

Block randomization over four blocks of 25 patients will be used to ensure an equal number of patients in each treatment group, even if the trial was terminated early for any reason. Two blocks will be reserved for patients with quiescent/minimal disease and two blocks for patients with mild disease, in order to ensure an equal number of these patients in each treatment group. Patients will be randomised (1:1) to receive Frondanol (one 1000 mg capsule twice daily) or placebo (in a similar capsule) as an adjunct to their standard therapy using a randomization number sequence generator. This will be conducted by the study statistician using the Microsoft Excel random number generator and will only be shared with the study coordinator.

All patients and investigators, excluding the study coordinator, will be blinded to treatment allocation. Frondanol and placebo capsules will be placed in identical-looking vials which will be labelled with the study name and number, and no identifying information. The labelling of the vials will be done with the open randomization sheet by the study coordinator. When a patient agrees to participate, and signs the informed consent form, the physician will assign to the patient the next available randomization number from the randomization sheet (supplied by the study coordinator) with the corresponding labelled medication vial. Patients will be instructed to take one capsule of their assigned medication twice daily. Hence, capsules will be given in a double-blind manner where patient and physician are not aware of treatment allocation as the treatment and placebo vials will only indicate the pilot study name. Investigators involved in the laboratory analysis of samples will also be blinded, they will only know if a patient belongs to group 1 or 2 but will not know which group is taking Frondanol and which is taking placebo.

RJ

Version 3.2. Effective Date: 04 December 2021

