6.4 Study population

One hundred patients (50 per arm) with stable IBD (Crohn's disease or ulcerative colitis, in remission) will be recruited in one of the participating study centres (Mediclinic City Hospital, Mediclinic Parkview Hospital, Rashid Hospital) by one of the coinvestigator consultant gastroenterologists.

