6.5 Eligibility criteria

- **Inclusion criteria:**

A confirmed clinical diagnosis of IBD of any duration, age 18 years or older, with mild to moderate disease and on standard therapy. The diagnostic criteria for IBD include the presence of chronic diarrhoea for more than four weeks, and evidence of active inflammation on endoscopy and chronic changes on biopsy. Patients with stable mild to moderate IBD will be eligible for the study. Stable IBD is defined as having stable symptoms over a period of several weeks, diagnostic evaluation has been completed and the patient has been on consistent medication. Mild to moderate IBD is indicated by a Partial Mayo score (Mayo Clinic Score/Disease Activity Index for Colitis) of between 1-6, and a total of Mayo score of 1-10 (Pabla and Schwartz, 2020). For patients with Crohn's disease, only those with Crohn's colitis will be included (patients with small bowel disease are eligible to enter the trial as long as they also have large bowel inflammation).

- **Exclusion criteria:**

Pregnancy, breastfeeding, allergy to seafood or marine products, severe medical illness such as uncontrolled diabetes ($\text{HbA1C}>10$), significant or unstable cardiovascular or pulmonary disease, impaired renal function ($\text{Cr}>2.0\text{mg/dL}$), current or recent (<1 year) malignancy, or other significant medical illness that in the view of the investigators may impair participation in the study. Patients with severe IBD (defined by a Partial Mayo score of 7-9 and a total Mayo score of 11-12 (Pabla and Schwartz, 2020), with active symptoms) will not be eligible to participate in the study.

Reference:

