8.2 Statistical methods

All statistical analyses will be carried out using SPSS Software (Armonk, New York, USA). Potential confounders such as age and sex will be controlled for during the analysis phase. A per-protocol analysis including only participants who have a full data set will be used to assess the efficacy of Frondanol treatment in lowering inflammatory markers. An intention-to-treat analysis will also be conducted including patients who drop out before the study ends, for whom we will use last observation carried forward (LOCF) i.e. we will impute the last observed data for all subsequent (missing) observation points. For quantitative data, within-group and between-group comparisons will be analyzed using the General linear Repeated Model (MANOVA), which would allow for adjustment of potential confounders such as age and sex. Data will be plotted as mean \pm SEM and p values <0.05 will be considered statistically significant.

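### The protocol gives three population descriptions that do not match for a trial of lowering inflammation, and its analysis does not say how baseline disease activity will be handled

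*Combined protocol and SAP*

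**What the plan says.** The protocol describes who is to be studied in three ways.

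- **In remission.** The design overview (numbered 5.1, within section 6) states the aim as testing efficacy "in decreasing bowel inflammation in patients with a clinical diagnosis of IBD who are in remission and on standard of care treatment". The Protocol Summary repeats this. Section 3 describes patients "who are currently in remission and are on standard therapy", and section 6.4 says that patients with Crohn's disease or "ulcerative colitis, in remission) will be recruited".
- **Mild to moderate.** Section 6.5 and the Protocol Summary state: "Patients with stable mild to moderate IBD will be eligible for the study". The numerical rule is a Partial Mayo score "of between 1-6, and a total of Mayo score of 1-10".
- **Quiescent/minimal or mild.** Section 6.3 plans four blocks of 25. "Two blocks will be reserved for patients with quiescent/minimal disease", and the other two are for mild disease. No block is named for moderate disease, and no cut-off between the strata is given.

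On inflammation at entry, section 6.5 lists active endoscopic inflammation among the criteria for diagnosing IBD of any duration, without a date. Crohn's patients must have Crohn's colitis. No threshold is set for fecal calprotectin, CRP, endoscopy or histology at T0. Section 6.13 lists a baseline endoscopy for every patient. Section 6.2 only hopes that colonoscopies can be timed around treatment, and Table 2 takes T0 tissue only if a routine colonoscopy happens.

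In section 8.2, the analysis of participants with complete data is meant "to assess the efficacy of Frondanol treatment in lowering inflammatory markers", and an intention-to-treat analysis is added. Age and sex are the only covariates named, as examples. The activity strata, baseline marker levels and any interaction with treatment are not mentioned.

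**The concern.** An aim of decreasing inflammation needs patients with some inflammation to decrease. If a share of those enrolled already have low marker levels on standard therapy, they can contribute little or no fall, and an average over everyone understates any effect in the rest.

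The population mismatch makes this harder to judge. Sites cannot tell from the protocol whether a patient with moderate activity is wanted. Whoever randomises has no block for such a patient. A reader of the result would not know whether it applies to remission, to mild disease or to mild-to-moderate disease. The benefit that sections 3 and 10.2 hope for, a better chance of staying in remission, is not among the objectives in section 5.

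**Working it through.** **1. The three descriptions side by side**

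| Place | Population | Can include moderate disease? |
|---|---|---|
| Summary, 3, 5.1, 6.4 | in remission | no |
| Summary, 6.5 | mild to moderate, Partial Mayo 1-6, total Mayo 1-10 | yes |
| 6.3 | quiescent/minimal or mild | no block provided |

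The protocol does not define remission or quiescent/minimal by score, so the descriptions may overlap at low scores. They cannot agree at the moderate end. At the other end, a score of 0 is outside the eligibility range, and section 6.3 does not say whether quiescent is meant to include it.

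**2. Planned mix**

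Four blocks × 25 = 100 places, which matches "One hundred patients (50 per arm) with stable IBD". Quiescent/minimal disease takes 2 × 25 = 50 places, or 50%.

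**3. Is there a planned power to reproduce?**

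No. Section 8.1 is headed as a sample size and power calculation but contains only recruitment and randomisation text. It gives no effect size, SD, power or dropout rate, so the 100 cannot be reproduced.

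**4. Illustration of dilution (assumed inputs)**

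From the protocol: 50 per arm and a 0.05 significance level. Assumed: a two-sided test, SD = 1, an effect d in patients who can respond, none in a share f at the floor, and equal SD in both groups.

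- Pooled effect = d × (1 − f)
- Standard error = √(2/50) = 0.20
- Power ≈ Φ(pooled effect / 0.20 − 1.96)
- n per arm for 80% power = 2 × (1.96 + 0.84)² / (pooled effect)²

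The effect detectable with 80% power is (1.96 + 0.84) × 0.20 = 0.56 SD. Starting there (unrounded values carried):

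| Share at floor f | Pooled effect | Power | n per arm for 80% |
|---|---|---|---|
| 0% | 0.56 | 80% | 50 |
| 25% | 0.42 | 56% | 89 |
| 50% | 0.28 | 29% | 200 |
| 75% | 0.14 | 10% | 800 |

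At f = 50%, for d from 0.4 to 0.8 SD, power falls from 52%-98% to 17%-52%.

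**5. Sensitivity to the equal-SD assumption**

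Patients at a floor would probably vary less. Let their SD be s times that of the others, with f = 50% and d = 0.56. The control variance is 0.5 + 0.5s². The treated variance adds f(1 − f)d² = 0.25 × 0.56² = 0.078 for the mixture of effects.

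- s = 1: SE = √((1 + 1.078)/50) = 0.204, power Φ(0.28/0.204 − 1.96) = 28%
- s = 0.5: SE = √((0.625 + 0.703)/50) = 0.163, power 40%
- s = 0: SE = √((0.5 + 0.578)/50) = 0.147, power 48%

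Dilution remains in each case, but its size depends on quantities that the documents do not give.

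**6. Precision of an interaction**

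If the strata fill as planned, each has 25 per arm. The difference between the two stratum effects has SE √(4 × 1/25) = 0.40 SD, twice that of the main comparison, and a 95% interval of about ±1.96 × 0.40 = ±0.78 SD.

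**The case against.** Several stronger readings are tempting, and the documents do not support them.

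*That no current inflammation is required at entry.* Section 6.5 does set a floor: a Mayo score of at least 1, Crohn's colitis for Crohn's patients, and large bowel inflammation for those who also have small bowel disease. The floor is weak, because a total of 1 qualifies, no particular item must score, and the Crohn's condition has no measure or date. It still exists.

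*That many patients have nothing to lower.* No baseline marker level is given. Quiescent disease is not shown to mean normal plasma cytokines, tissue expression or eicosanoids, and section 3 presents Frondanol as treating chronic inflammation that persists beneath remission.

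*That a null result could not be interpreted.* The objectives compare levels between arms. If placebo patients worsen, a difference can appear without any fall on Frondanol. Symptoms, Mayo score, IBDQ and fecal calprotectin are scheduled at T0, T1 and T2, and activity is a randomisation stratum. The data needed to look at this will be collected; what is missing is a prespecified analysis. Pooling over strata is itself an inference from the silence of section 8.2.

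*That the main analysis, or entry, should be restricted to raised calprotectin.* This would select patients for more than 20 plasma and tissue markers on one stool marker, with a limit that the protocol does not state. It would drop patients whose other markers are raised and add regression to the mean to the within-group comparisons. Any power gain depends on the floor share and floor SD, both unknown.

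It is also fair that this is a pilot with no stated power, so no planned power is lost. What remains is the mismatch between population, eligibility and strata, and the silence on baseline activity in an analysis that tests efficacy at p < 0.05.

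**Conclusion.** The concern holds in two parts. First, the stated population, the eligibility criteria and the randomisation strata contradict one another. This needs no assumption: eligible moderate patients have no block, and the population to which the result applies is undefined. Second, with half the places reserved for quiescent/minimal disease, no marker or dated endoscopic minimum at T0, and no baseline activity in the analysis model, a floor effect could dilute the comparison of marker lowering. That is a risk, not a demonstrated loss. The power figures above rest on assumed effects, floor shares and SDs and are not properties of this trial. The point should be settled before the analysis is fixed; it does not show that the trial cannot answer its question.

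**What to change.** 1. **Reconcile the population.** Bring the Protocol Summary, section 3, the design overview (5.1) and sections 6.3, 6.4 and 6.5 into line, so that the described population, the eligibility rule and the strata match and every eligible patient belongs to a defined stratum. State the scores that separate the strata. Which population is intended is for the investigators to say.

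2. **Amend section 8.2.** Keep all randomised patients in the main comparison whatever their baseline level. Add the randomisation activity stratum and each marker's T0 value as covariates. With T0 as a covariate, the modelled outcomes are the later visits only.

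3. **Prespecify one treatment-by-baseline term**, using T0 fecal calprotectin or the activity stratum, and show results by baseline level as a supporting analysis.

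Cost: protocol wording and slightly more analysis, using values already scheduled, with no change to patient numbers or visits. The interaction will be imprecise with 50 per arm, so it should be reported as an estimate with its interval and not read as a test. T0 tissue values will be missing where no routine colonoscopy is done, so for tissue markers the plan should say how the stratum or calprotectin stands in.
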